10.3.3. Safety Monitoring

The Lilly CRP will monitor safety data throughout the course of the study.

Lilly will review SAEs within time frames mandated by company procedures. The Lilly CRP will, as is appropriate, consult with the functionally independent Global Patient Safety therapeutic area physician or clinical scientist, and review:

- trends in safety data

- laboratory analytes
- AEs

If a patient experiences elevated ALT $>5\times$ ULN and elevated total bilirubin $>2\times$ ULN, clinical and laboratory monitoring should be initiated by the investigator. For patients entering the study with ALT $>2\times$ ULN, monitoring should be triggered at ALT $>2\times$ baseline.

Details for hepatic monitoring depend upon the severity and persistence of observed laboratory test abnormalities. To ensure patient safety and comply with regulatory guidance, the investigator is to consult with the Lilly CRP regarding collection of specific recommended clinical information and follow-up laboratory tests. See [Attachment 4](#).

In the event that safety monitoring uncovers an issue that needs to be addressed by unblinding at the group level, only members of the assessment committee (an advisory group for this study formed to protect the integrity of data; refer to [Section 12.2.14](#)) can conduct additional analyses of the safety data.

10.3.4. Complaint Handling

Lilly collects product complaints on study drugs used in clinical trials in order to ensure the safety of study participants, monitor quality, and to facilitate process and product improvements.

Complaints related to unblinded comparator drugs or concomitant drugs are reported directly to the manufacturers of those drugs/devices in accordance with the package insert.

For blinded studies, all product complaints associated with material packaged, labeled, and released by Lilly or its designee will be reported.

The investigator or his/her designee is responsible for handling the following aspects of the product complaint process in accordance with the instructions provided for this study:

- recording a complete description of the product complaint reported and any associated AEs using the study-specific complaint forms provided for this purpose
- submit the completed product complaint form within 24 hours to Lilly or its designee

If the investigator is asked to return the product for investigation, he/she will return a copy of the product complaint form with the product.

10.4. Sample Collection and Testing

[Attachment 1](#) lists the schedule for sample collections in this study.

[Attachment 2](#) lists the specific tests that will be performed for this study and whether these will be performed at a central or local laboratory.

A deviation from the cerebrospinal fluid (CSF) and PK sampling schedule will not be considered a protocol violation.

10.4.1. Samples for Study Qualification and Health Monitoring

Blood, urine, CSF, bone marrow, and tissue samples will be collected to determine whether patients meet inclusion/exclusion criteria, to monitor patient health, and to characterize the malignancy.

From T-ALL patient a bone marrow biopsy will be taken by core needle biopsy. A small amount of archived paraffin tissue block and bone marrow previously obtained will be requested from T-LBL patients. A small amount of archived lymph node tissue or slides with unstained tumor sections are required. For both T-ALL and T-LBL patients, due diligence should be used to make sure that tumor and/or bone marrow specimen (not a normal adjacent or a tumor margin sample) are provided. Pathology notes accompanying archival tissue may also be requested.

Investigators must document their review of each laboratory safety report.

Samples collected for specified laboratory tests will be destroyed within 60 days of receipt of confirmed test results. Tests are run and confirmed promptly whenever scientifically appropriate. When scientific circumstances warrant, however, it is acceptable to retain samples to batch the tests run, or to retain the samples until the end of the study to confirm that the results are valid. Certain samples may be retained for a longer period, if necessary, to comply with applicable laws, regulations, or laboratory certification standards.

10.4.2. Samples for Pharmacodynamics and/or Biomarkers

There is growing evidence that genetic variation may impact a patient's response to therapy. Variable response to therapy may be due to genetic determinants that impact drug absorption, distribution, metabolism, and excretion, the mechanism of action of the drug, the disease etiology and/or the molecular subtype of the disease being treated. Therefore, where local regulations and ERBs allow, a blood sample will be collected for pharmacogenetic analysis.

Collection of samples for exploratory biomarker research is also part of this study. Blood, CSF, EDTA plasma, tissue, and bone marrow samples will be collected.

Required samples for biomarker research to be collected from all patients in this study are the following:

- whole blood
- EDTA plasma
- archived bone marrow aspirate/biopsy samples from T-ALL patients
- on study bone marrow aspirate/biopsy samples from T-ALL patients
- archived tumor tissue from T-LBL patients

Optional samples for biomarker research that should be collected from patients in the study where possible are the following:

- on study pretreatment and posttreatment tumor tissue from T-LBL patients
- tumor tissue at time of disease progression or if deemed necessary by the investigator
- CSF (adult patients in Phase 1 only)

Samples will be tested for markers of Notch and related pathway activation including, but not limited to, protein expression and activation by immunohistochemistry and ELISA, and gene expression by quantitative polymerase chain reaction (PCR) analysis to evaluate their association with the observed clinical outcomes to LY3039478, as well as circulating A-beta peptides. Samples will also be tested for miRNA and transcriptome expression.

In the event of an unexpected AE or the observation of unusual response, the pharmacogenetic biomarker samples may be genotyped and analysis may be performed to evaluate a genetic association with response to LY3039478. These investigations may be limited to a focused candidate gene study or, if appropriate, wider analysis of multiple genes and/or regions may be performed to identify regions of the genome associated with the variability observed in drug response. The pharmacogenetic biomarker samples will only be used for investigations related to disease and drug or class of drugs under study in the context of this clinical program. They will not be used for broad exploratory unspecified disease or population genetic analysis.

Other samples may be used for research to develop methods, assays, and/or companion diagnostics related to T-ALL, Notch gene, and Notch gene pathway and related pathways.

Bone marrow or tissue biopsy will be taken by core needle biopsy and/or surgical biopsy.

A small amount of archived bone marrow/tissue or slides with unstained tumor sections are required for biomarker research.

Additionally, the optional tumor biopsies from T-LBL patients will be analyzed at laboratories using assays designated by the sponsor. Sample handling and shipment to the central laboratory will occur per instructions given to the study site.

The samples will be coded with the patient number and stored for up to a maximum 15 years after the last patient visit for the study at a facility selected by the sponsor. The samples and any data generated from them can only be linked back to the patient by investigator site personnel. The duration allows the sponsor to respond to regulatory requests related to the study drug.

Samples will be destroyed according to a process consistent with local regulation.

10.4.3. Samples for Drug Concentration Measurements

Pharmacokinetics

PK samples will be collected as specified in the Pharmacokinetic Sampling Schedule ([Attachment 3](#)).

Venous blood samples of approximately 3 mL each will be collected to determine the plasma concentrations of LY3039478 and dexamethasone. Separate blood samples are not required for LY3039478 and dexamethasone. After harvesting the plasma, samples will be divided into 2 approximately equal portions by site personnel, one for the determination of plasma concentrations of LY3039478, and the other for the determination of plasma concentrations of dexamethasone. Instructions for the collection and handling of blood samples will be provided by the sponsor. A maximum of 5 blood samples may be drawn at additional time points during

the study if warranted and agreed upon between both the investigator and Lilly. CSF samples will be used to determine the concentrations of LY3039478.

CSF concentrations of LY3039478, and plasma concentrations of LY3039478 and dexamethasone will be quantified using validated liquid chromatography-mass spectrometry / mass spectrometry (LC-MS/MS) assays. All bioanalytical samples will be stored in the United States. The remaining plasma samples collected for PK evaluation may be used for exploratory studies to assess the metabolism of LY3039478, which may involve sample pooling. These samples may be retained for a maximum of 2 years following the last patient visit for the study.

11. Data Quality Assurance

To ensure accurate, complete, and reliable data, Lilly or its representatives will do the following:

- provide instructional material to the study sites, as appropriate
- sponsor start-up training to instruct the investigators and study coordinators. This session will give instruction on the protocol, the completion of the CRFs, and study procedures.
- make periodic visits to the study site
- be available for consultation and stay in contact with the study site personnel by mail, telephone, and/or fax
- review and evaluate CRF data and use standard computer edits to detect errors in data collection
- conduct a quality review of the database

In addition, Lilly or its representatives will periodically check a sample of the patient data recorded against source documents at the study site. The study may be audited by Lilly or its representatives, and/or regulatory agencies at any time. Investigators will be given notice before an audit occurs.

To ensure the safety of participants in the study, and to ensure accurate, complete, and reliable data, the investigator will keep records of laboratory tests, clinical notes, and patient medical records in the patient files as original source documents for the study. If requested, the investigator will provide Lilly, applicable regulatory agencies, and applicable ERBs with direct access to original source documents.

11.1. Data Capture System

An electronic data capture system will be used in this trial. The site maintains a separate source for the data entered by the site into the sponsor-provided electronic data capture system.

CRF data collected by the third-party organization (TPO) will be encoded by the TPO and stored electronically in the TPO's database system. Validated data will subsequently be transferred to the Lilly data warehouse, using standard Lilly file transfer processes.

Data managed by a central vendor, such as laboratory test data or ECG data, will be stored electronically in the central vendor's database system. Laboratory data will be transferred from the central vendor to the Lilly generic labs system.

Any data for which the paper documentation provided by the patient will serve as the source document will be identified and documented by each site in that site's study file. Paper documentation provided by the patient may include, for example, a paper diary to collect patient-reported outcome measures (eg, a rating scale), a daily dosing schedule, or an event diary.

Data from complaint forms submitted to Lilly will be encoded and stored in the global product complaint management system.

12. Sample Size and Statistical Methods

12.1. Determination of Sample Size

Approximately 86 to 92 patients will be enrolled in this multicenter study.

In the Phase 1 portion of the study, the primary objective is to determine the MTD and the recommended dose for Phase 2. Approximately 13 to 16 patients will be enrolled into the adult (Part A), and approximately 13 to 16 patients will be enrolled in the pediatric (Part B) cohorts sequentially and without randomization to dose. The total sample size per cohort will be determined by DLTs.

In the Phase 2 portion of the study, the primary objective of this study is to compare the ORR (CR plus CRi) rate between LY3039478 administered with dexamethasone and placebo administered with dexamethasone, in adult patients with relapsed/refractory T-ALL/T-LBL. Approximately 60 evaluable patients will be randomized to the 2 treatment arms in a 2:1 ratio (40 randomized to LY3039478 and dexamethasone and 20 randomized to placebo and dexamethasone).

Assuming the ORR for the LY3039478 and dexamethasone arm is 40% and the ORR of the placebo and dexamethasone is 5%, the sample size of 60 evaluable patients will give approximately 82% statistical power to detect the difference, using a 2-sided Fisher's test at the significance level of 0.05, with 1 futility interim once the 30th enrolled patient completes the remission status determination (Section 12.2.14).

Primary analysis for ORR will be conducted once the last patient enrolled has completed 3 cycles of treatment, discontinued treatment, started new anticancer therapy or met criteria for objective progression. Patients who are randomized and do not achieve a CR or CRi will be considered as nonresponders in the primary analysis for ORR.

12.2. Statistical and Analytical Plans

12.2.1. General Considerations

Statistical analysis of this study will be the responsibility of Lilly.

Efficacy analyses will be based on the intention-to-treat (ITT) analysis set. This population is defined as all patients randomized to study treatment. Patients will be grouped according to dose level cohort or randomized treatment. Sensitivity analyses may be conducted (if applicable) excluding patients that are randomized but do not receive treatment, and by actual treatment received.

A secondary analysis of the primary efficacy endpoint based upon the per-protocol set (PPS) of patients may be performed if there are significant numbers of patients with major protocol deviations ($\geq 10\%$ of total patient population). The PPS is defined as those patients in the ITT set who are compliant with the study protocol. Major deviations from the protocol for purposes of this analysis will be detailed in the Statistical Analysis Plan.

Safety analyses will be based on the safety population, defined as all enrolled patients receiving at least 1 dose of any study drug. Patients will be grouped according to treatment received in Cycle 1.

PD and/or tailoring biomarker analyses will be based on the subset of patients from the above populations from whom a valid assay result (according to laboratory guideline) has been obtained.

All tests of treatment effects will be conducted at a 2-sided alpha level of 0.05, unless otherwise stated. All tests of interactions will be conducted at a 2-sided alpha level of 0.1, and all CIs will be given at a 2-sided 95% level, unless otherwise stated.

Any change to the data analysis methods described in the protocol will require an amendment ONLY if it changes a principal feature of the protocol.

Before unblinding of the aggregate database, minor modifications or clarifications to the data analysis methods may be described and justified in the statistical analysis plan.

Any other change to the data analysis methods described in the protocol, and the justification for making the change, will be described in the clinical study report.

The assumptions for each statistical method will be evaluated. If there is violation of assumptions, alternative statistical methods may be used.

Additional exploratory analyses of the data will be conducted as deemed appropriate.

12.2.2. Patient Disposition

A detailed description of patient disposition will be provided. It will include a summary of the number and percentage of patients entered into the study, enrolled in the study, and treated as well as number and percentage of patients completing the study, or discontinuing (overall and by reason for discontinuation). A summary of all important protocol deviations will be provided.

12.2.3. Patient Characteristics

Patient demographics including age, sex, screening height and weight, and screening body mass index will be reported using descriptive statistics.

Baseline disease characteristics will be summarized by presenting frequency counts and percentages including initial diagnosis (T-ALL or T-LBL), T-ALL subtypes, ECOG performance status, disease status at study entry (refractory or relapse), Notch and FBWX7 mutational status, duration of first remission, number of prior courses of induction therapy, extramedullary disease, and history of CNS leukemia. Other patient characteristics will be summarized as deemed appropriate.

12.2.4. Concomitant Therapy

Concomitant medications will be summarized for the safety population.

12.2.5. Postdiscontinuation Therapy

The numbers and percentages of patients reporting postdiscontinuation therapies will be provided overall, by type of therapy (surgery, radiotherapy, systemic therapy, or stem cell transplant), and by drug name.

In the Phase 2 portion, numbers and percentages of patients randomized to placebo and dexamethasone who following treatment discontinuation receive LY3039478 and dexamethasone will be included in summaries of postdiscontinuation therapies.

12.2.6. Treatment Compliance

The number of dose omissions, reductions, delays, and cycles received and the dose intensity will be summarized for all treated patients per treatment arm. Summarized data will be provided for the period prior to first CR, the period following first CR, and the total treatment period.

Treatment compliance information for study drug will be collected through pill counts at each visit and the number of tablets taken relative to the number expected to be taken will be summarized.

12.2.7. Primary Outcome and Methodology

In the Phase 1 portion, the primary outcome of interest is determining the MTD and recommended dose for Phase 2.

In the Phase 2 portion, the primary efficacy endpoint of ORR (CR plus CRi) rate and its exact 95% confidence interval (CI) will be estimated for each treatment arm. The proportion in each treatment arm will be compared using Fisher's exact test. All randomized patients, according to the ITT principle, will be included in the analysis of this endpoint.

Sensitivity analyses of the primary outcome measure will include a re-randomization test.

12.2.8. Other Analyses of Efficacy

No formal efficacy analysis is planned for the Phase 1 portion of this trial. However, any response data will be listed and tabulated.

In Phase 2, the following secondary efficacy parameters will be summarized for each treatment arm:

- Proportion of patients achieving a ORR or PR
- Proportion of patients achieving a CR, CRi, and PR
- OS
- RFS
- EFS
- DoR

The secondary efficacy endpoints of proportion of patients achieving ORR plus PR, and PR, and their exact 95% CIs will be estimated for each treatment arm and compared by 2-sided Chi-squared test or Fisher's exact test between 2 arms. A Fisher's exact test will be chosen over

a Chi-squared test if in the 2x2 table, any of the expected cell counts are less than 5, or any cell has zero counts.

For the secondary efficacy endpoints OS, RFS, and EFS, the Kaplan-Meier method (Kaplan and Meier 1958) will be used to estimate the survival curves as well as survival rates at various prespecified time points (12 months for OS, 6 and 12 months for RFS and EFS) for each treatment arm.

The secondary efficacy endpoint DoR is subject to competing risk of death without relapse; therefore, the cumulative incidence of relapse (Gray 1988; Pepe and Mori 1993; Gooley et al. 2001) will be used. In the calculation, patients who did not have the event will be considered right-censored observations. All randomized patients, according to the ITT principle, will be included in the analysis of these endpoints.

The comparison of the survival curves between treatment groups will be conducted by a log-rank test. Exploratory analyses for the comparison of the survival curves between treatment groups may be conducted by a stratified log-rank test with some of the following stratification variables: initial diagnosis (T-ALL phenotype, T-LBL), response to last therapy (refractory or relapsed), age, number of prior therapies (≤ 2 , > 2), NOTCH-1/FBXW7/RAS/PTEN status.

The Cox proportional hazard model (Cox 1972) with treatment as a factor will be used to estimate the hazard ratio and corresponding 95% CI with Wald's test p-value after adjusting for the following potential predictive/prognostic variables: initial diagnosis (T-ALL phenotype, T-LBL), response to last therapy (refractory or relapsed), age, number of prior therapies (≤ 2 , > 2), NOTCH-1/FBXW7/RAS/PTEN status.

All randomized patients, according to the ITT principle, will be included in the analysis of these endpoints.

For the analysis of time-to-event endpoints, a sensitivity analysis censoring the event time at the date of SCT will be completed to evaluate the potential impact from imbalance in patients receiving transplantation between the study arms.

No missing data will be imputed.

Efficacy data (CR, CRi, PR, and ORR) for patients receiving patients receiving LY3039478 in combination with dexamethasone after failure of placebo in combination with dexamethasone will be tabulated, and further exploratory analyses of efficacy data conducted as warranted.

Additional exploratory analyses may be performed as deemed appropriate.

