All tests of treatment effects will be conducted at a 2-sided alpha level of 0.05, unless otherwise stated. All tests of interactions will be conducted at a 2-sided alpha level of 0.1, and all confidence intervals (CIs) will be given at a 2-sided 95% level, unless otherwise stated.

Efficacy:

No formal efficacy analysis is planned for the Phase 1 portion of this trial. However, any response data will be listed and tabulated. In the Phase 2 portion, the primary efficacy endpoint of ORR (CR plus CRI) and its exact 95%

CI will be estimated for each treatment arm. The proportion in each treatment arm will be compared using Fisher's exact test. All randomized patients, according to the ITT principle, will be included in the analysis of this endpoint. The secondary efficacy endpoints of proportion of patients achieving an ORR plus PR, and PR, and their exact 95% CIs will be estimated for each treatment arm and compared by 2-sided Chi-squared test or Fisher's exact test between 2 arms. For the secondary efficacy endpoints OS, RFS, and EFS, the Kaplan-Meier method will be used to estimate the survival curves as well as survival rates at various prespecified time points (12 months for OS, 6 and 12 months for RFS and EFS) for each treatment arm. The secondary efficacy endpoint DoR is subject to competing risk of death without relapse; therefore, the cumulative incidence of relapse will be used. In the calculation, patients who did not have the event will be considered right-censored observations. All randomized patients, according to the ITT principle, will be included in the analysis of these endpoints. The comparison of the survival curves between treatment groups will be conducted by a log-rank test.

Safety: Safety analyses will include listings and/or summaries of the following:

- adverse events (AEs) and treatment-emergent adverse events (TEAEs),
- drug exposure,
- dose adjustments,
- laboratory measures,
- reasons for death, and
- hospitalizations and transfusions.

Health Outcomes: FACT-Leu results will be summarized descriptively by cycle, including number of completed questionnaires, scores for each scale and subscale, and changes from baseline.

Pharmacokinetics: PK analyses will be conducted on patients who receive at least 1 dose of the study drug and have samples collected. PK parameter estimates for LY3039478 and dexamethasone, where possible, will be calculated by standard noncompartmental methods of analysis.

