10.1.3.1. T-ALL

For T-ALL: PR rate is defined as a decrease of at least 50% in blast count on the bone marrow aspirate; PR requires all of the hematologic values for a CR but with a decrease of at least 50% in the percentage of blasts to 5% to 25% in the bone marrow aspirate. The proportion of patients achieving a PR is defined as the total number of patients achieving a PR divided by the total number of patients randomized in that arm.

DoR (CR and CRi) is measured from the date of CR or CRi by blood count recovery and bone marrow examination, until the date of relapse. It is measured until the date T-ALL relapse is detected. For patients who die without report of relapse, DoR is censored on the date of death, regardless of cause. For a patient with no report of relapse or death by the end of the follow-up data collection, observation is censored at the date of last contact prior to the data inclusion cutoff date.

Relapse-free survival (RFS) is defined as the timeframe before the reappearance of unequivocal leukemia blast cells in the blood or the bone marrow ($>5\%$), in the CNS (positive cytopspin examination of CSF) or in any other extramedullary site after a CR.

RFS is defined only for patients who achieve CR, and is measured from the date of attaining the leukemia-free state (as defined in Section 10.1.2) until the date of T-ALL relapse or death from

any cause, whichever occurs first. For a patient who is not known to have relapsed or died by the end of study follow-up, observation of RFS is censored at the date of last contact prior to the data inclusion cutoff date.

Event-free survival (EFS) is defined for all patients and measured from the date of entry on study. It is measured until treatment failure, relapse from CR, or death from any cause, whichever occurs first. For a patient with none of these events before the end of study follow-up, observation of EFS is censored at the date of last contact prior to the data inclusion cutoff date. If the patient does not achieve a CR, EFS is defined as the point of treatment failure or death, whichever comes first.

Refractory disease for T-ALL is defined as failure to achieve CR.

Relapsed disease for T-ALL is defined as the reappearance of the blast in the blood or bone marrow (>5%) or any extramedullary site after achievement of a CR.

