## 6.11. Efficacy Analyses

Efficacy analyses will be conducted on the ITT analysis set, with patients grouped according to randomized treatment.

The following are definitions of the primary and secondary efficacy endpoints:

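### Protocol 12.2.8 puts all randomized patients into the duration-of-remission analysis, although the endpoint starts at response; patients who cannot relapse would then distort the relapse incidence by arm

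*Protocol*

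**What the plan says.** Protocol 12.2.8 analyses DoR by cumulative incidence of relapse. The same paragraph then states: "patients who did not have the event will be considered right-censored observations. All randomized patients, according to the ITT principle, will be included". The all-randomized sentence appears again later in 12.2.8, and the Synopsis (Efficacy) has the same statement: "All randomized patients, according to the ITT principle, will be included in the analysis of these endpoints".

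The endpoint definitions start the clock at response:
- Protocol 10.1.3.1 (T-ALL): "DoR (CR and CRi) is measured from the date of CR or CRi by blood count recovery and bone marrow examination".
- Protocol 10.1.3.2 (T-LBL): from the time the criteria for CR or PR are met.
- SAP 6.11 (T-ALL): from the date of CR, CRi or PR.

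In all three, a patient without relapse is censored at death or last contact.

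SAP 6.11.3 repeats the cumulative-incidence and right-censoring sentences without the all-randomized sentence. SAP 6.11, however, opens with "Efficacy analyses will be conducted on the ITT analysis set, with patients grouped according to randomized treatment", and SAP 6.6 defines that set as all patients randomized. Both documents restrict RFS in words to patients who reach remission (for T-ALL, CR in Protocol 10.1.3.1; CR/CRi in SAP 6.11). Neither does so for DoR.

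**The concern.** The analysis set contradicts the definition. A never-responder has no DoR start date and no possible relapse, yet is to be included and right-censored. Such a patient stays in the denominator for as long as follow-up is credited and never contributes an event. The estimated incidence then becomes largely the product of the response rate and the relapse rate among responders. A drug that produces more remissions would show more relapse, and the figure would no longer describe how long remissions last. DoR is a named Phase 2 secondary objective, so the choice belongs in the plan and should not be left to programming once data exist.

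**Working it through.** **Inputs from the documents.** Protocol 12.1 assumes an ORR of 40% on LY3039478 plus dexamethasone and 5% on placebo plus dexamethasone, with "40 randomized to LY3039478 and dexamethasone and 20 randomized to placebo and dexamethasone".

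**The plan's own figure.** Protocol 12.1 states "approximately 82% statistical power to detect the difference", "using a 2-sided Fisher's test at the significance level of 0.05". An arcsine approximation with continuity correction gives 82.2%; exact enumeration of the two-sided Fisher test gives 87.8%. The figure is not in dispute. It only confirms the design inputs.

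**Patients who cannot relapse (CR/CRi).** 40 × (1 − 0.40) = 24 of 40 on LY3039478; 20 × (1 − 0.05) = 19 of 20 on placebo.

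**Crude arithmetic.** Let r be the relapse risk among responders, equal in both arms. Over all randomized patients the incidence is 0.40r v 0.05r, a ratio of 0.40/0.05 = 8 for any r. With r = 50%: 20% v 2.5%.

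**With censoring.** Assumptions not in the documents:
- relapse in responders is exponential, 50% by 12 months, in both arms;
- the death hazard in remission is 0.01 per month, censored at death;
- non-responders are censored at exponential times with the median shown;
- follow-up is 18 months.

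Large-sample 12-month estimates, and 40:20 log-rank tests (4,000 trials per row) that call LY3039478 significantly worse:

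| Non-responder median follow-up | LY3039478 | Placebo | Ratio | Log-rank, LY3039478 worse |
|---|---|---|---|---|
| 2 months | 40% | 16% | 2.4 | about 4-6% |
| 4 months | 32% | 6% | 5.0 | 22-23% |
| 8 months | 26% | 4% | 6.7 | about 42% |
| 24 months | 21% | 3% | 7.8 | 53-55% |
| Responders only | 50% | 50% | 1.0 | n/a |

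The 2-month row is relevant because inclusion criterion 9 asks only for a life expectancy of at least 2 months.

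**If PR counts as response.** Same model, assumed PR rate added to each arm:

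| PR per arm | 2-month median | 4-month median | 24-month median |
|---|---|---|---|
| 10% | 1.5 | 2.2 | 3.2 |
| 20% | 1.3 | 1.7 | 2.3 |

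**Different assumptions, same direction.** Take a median of 6 months to relapse and 24 months to death in remission, non-responder median survival of 2, 4 or 8 months, and 24 months of follow-up. Censoring deaths gives ratios of 2.4, 5.5 and 6.9. Treating death as a competing event gives 26% v 3.3%, a ratio of about 8. The problem is therefore separate from how deaths are coded. If non-responders are censored at time zero, the ratio returns to 1.0.

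**Information on placebo.** Expected CR/CRi responders: 20 × 0.05 = 1. Chance of none: 0.95^20 = 36%.

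**The case against.** The strongest reply is that the rule would never be run as written. DoR has no start date for a never-responder, and Protocol 12.2.8 says missing data will not be imputed. SAP 6.11.3 omits the all-randomized sentence, and the Protocol allows the SAP to clarify methods. The ITT line in SAP 6.11 cannot mean that every patient enters every endpoint, because the same section limits RFS to patients with CR/CRi; it may mean only that patients are grouped as randomized.

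This has force on size, not on the defect. An omitted sentence is not a restriction: the SAP limits RFS in words and does not do so for DoR, while the Protocol states the opposite in the DoR paragraph itself. Dropping non-responders would be sensible, but it would depart from the written Protocol.

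Two stronger readings are tempting. A reader might infer that LY3039478 would show a five- to eight-fold excess of relapse. The documents do not support a fixed range: they give non-responders no clock, short follow-up brings the ratio down to 2.4, and the DoR objective, the T-LBL definition and the SAP T-ALL definition all count PR. A reader might also infer a high rate of false significance against LY3039478. That needs the log-rank test to apply to DoR. Both documents attach that test to survival curves, the term they use for the Kaplan-Meier analyses of OS, RFS and EFS, whereas DoR gets cumulative incidence and an objective worded as assessment.

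**Conclusion.** The point holds as a contradiction between endpoint definition and analysis set, with a known direction of error if the written rule is followed: the arm with more remissions shows more relapse. Assuming the design ORRs are true and relapse risk among responders is equal, the false ratio is about 2.4 to 8 for CR/CRi, and about 1.3 to 3.2 if PR counts at an assumed 10-20% per arm. It is 1.0 if non-responders are given zero time. If the log-rank test is read as covering DoR, which is not clear, rejection against LY3039478 runs from about 5% to 55% under the 50%-at-12-months model; other relapse and follow-up assumptions would move that range. The primary ORR analysis is unaffected. This should be corrected before the DoR analysis is programmed.

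**What to change.** 1. In Protocol 12.2.8 and the Synopsis, limit the all-randomized sentence to OS, EFS and the response rates. Say openly that RFS and DoR are analysed in the patients for whom they are defined.
2. For RFS, reconcile the T-ALL population: CR in Protocol 10.1.3.1 against CR/CRi in SAP 6.11.
3. In Protocol 12.2.8 and SAP 6.11.3, state that DoR is estimated only in documented responders, from the date of response.
4. Reconcile whether PR counts for T-ALL: the DoR objective (Protocol 6.2) and SAP 6.11 include it; Protocol 10.1.3.1 does not.
5. Report DoR descriptively by arm, with EFS and OS as the randomized comparisons.

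The cost is Protocol and SAP wording; no data collection or sample size changes. The drawback is that the placebo DoR curve may rest on about 1 CR/CRi patient, with a 36% chance of none. That limit is in the data already, and adding non-responders to the denominator only hides it.
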